**MC2-01-C6_STATISTICAL ANALYSIS PLAN_Final 3.0_07 September 2020**

Blood pressure and pulse rate will be taken with the subject in the sitting position with approximately 5 minutes' rest prior to measurement. Body temperature (oral or ear) will be also be measured.

Vital signs (pulse rate (beats/minute), and systolic and diastolic blood pressure (mm Hg), and oral or tympanic temperature (°C)), body weight (kg), body height (cm) and BMI (kg/m²) results will be presented in accordance with section 7.

Vital signs results will be presented by visit of assessment as scheduled in the Table 1.

Notable ranges are defined for vital signs according to Table 3.1. Notable values are post-baseline values outside the notable ranges, whether above or below, and are indicated as *notably abnormal*.

Table 3.1: Definition of Notable Ranges of Vital Signs

| Parameter | Notable Values and Changes from Baseline |
|--------------------------|---|
| Systolic blood pressure | 90 mmHg or lower and decreased by 20 mmHg or more, 180 mmHg or greater and increased by 20 mmHg or more |
| Diastolic blood pressure | 50 mmHg or lower and decreased by 15 mmHg or more, 110 mmHg or greater and increased by 15 mmHg or more |
| Pulse rate | 50 bpm or lower and decreased by 15 bpm or more, 120 bpm or greater and increased by 15 bpm or more |

Normal ranges are defined for vital signs according to Table 3.2.

MC2-01-C6_STATISTICAL ANALYSIS PLAN_Final 3.0_07 September 2020

Table 3.2: Definition of Normal Ranges of Vital Signs

| Parameter | Units of Measure | Age | | | Normal Ranges | |
|--------------------------|------------------|-----|-----|------|---------------|------|
| | | Any | Low | High | Low | High |
| | | | | | | |
| Systolic blood pressure | mmHg | - | 12 | 17 | 80 | 160 |
| Diastolic blood pressure | mmHg | - | 12 | 17 | 50 | 100 |
| Pulse rate | Beats/min | - | 12 | 17 | 50 | 100 |
| Oral temperature | °C | - | 12 | 17 | 35.0 | 37.5 |
| Tympanic temperature | °C | - | 12 | 17 | 35.0 | 37.5 |

Vital signs and body weight results will be presented as the following outputs:

- descriptive statistics for measured values and changes from baseline (vital signs, body weight, body height, BMI) by visit and highest/lowest post-baseline assessment (vital signs);
- frequency table for Out of range values, including frequency of Low and High values by visit and at any post-baseline assessment (vital signs);
- frequency table for notably abnormal values and changes from baseline (systolic blood pressure, diastolic blood pressure, pulse rate) by visit and at any post-baseline assessment.

All data will be listed. Notable values will be flagged.

ECG

eCRF form “ELECTROCARDIOGRAM”.

A 12-lead ECG will be recorded at visits indicated in Table 1. Recording will take place after 5 minutes’ rest in supine position. Recordings will be promptly transmitted to the central ECG vendor for interpretation. Additional (unscheduled) ECGs can be recorded for safety reasons at any time based on the judgement of the investigator.

Heart rate (beats/min), RR interval (msec), PR interval (msec), QRS duration (msec), QT interval (msec), QTC-F interval (msec), QTC-B interval (msec) will be summarized using standard descriptive statistics for continuous variables in accordance with section 7.

Notable ranges are defined for electrocardiogram according to Table 4. Notable values are post-baseline values outside the notable ranges and are indicated as *notably abnormal*.

**MC2-01-C6_STATISTICAL ANALYSIS PLAN_Final 3.0_07 September 2020****Table 4: Definition of Notable Ranges of ECG**

| Parameter | Notable Values and Changes from Baseline |
|-----------|---|
| QTc | QTc interval > 450 msec |
| | QTc interval > 480 msec |
| | QTc interval > 500 msec |
| | QTc interval increases from baseline >30 msec |
| | QTc interval increases from baseline >60 msec |

A 12-lead electrocardiogram (ECG) results will be presented in accordance with section 7 by visit of assessment as scheduled in the Table 1 as the following outputs:

- frequency table for Normal/Abnormal clinically significant (Abnormal CS) / Abnormal non-clinically significant (Abnormal NCS) evaluation for General assessment (Total assessment) by visit and any post-baseline Abnormal and clinically significant Abnormal assessment;
- frequency table for notably abnormal values and changes from baseline (QTC-F interval, msec; QTC-B interval, msec) by visit and any post-baseline notably abnormal value;
- descriptive statistics of ECG parameters and their changes from baseline (Heart rate, beats/min; RR interval, msec; PR interval, msec; QRS duration, msec; QT interval, msec; QTC-F interval, msec; QTC-B interval, msec) by visit and highest/lowest post-baseline value.

All ECG data will be listed. Notable values will be flagged.

Physical examinations

eCRF form: “PHYSICAL EXAMINATION”.

An abbreviated physical examination including general appearance, regional lymph nodes and a complete dermatological examination of the skin must be performed as scheduled in the Table 1.

Physical examination / dermatological examination results will be presented in accordance with section 7 by visit of assessment as the following output:

- frequency table for Normal/Abnormal clinically significant (Abnormal CS) / Abnormal non-clinically significant (Abnormal NCS) evaluation.

All physical examination / dermatological examination data will be listed.

**MC2-01-C6_STATISTICAL ANALYSIS PLAN_Final 3.0_07 September 2020**Local skin reactions

The local skin reaction assessment involves signs assessed by the investigator or designee and symptoms reported by the subject.

The investigator will assess the treatment area and/or immediate surrounding for the following identified signs:

- Perilesional erythema, scaling, edema, atrophy, vesicles and erosion/ulceration;
- Lesional vesicles, and erosion/ulceration.

The intensity of each local skin reaction category is to be graded according to the scale provided in Table 7-4 of the protocol. The most severe intensity observed for each category of the local skin reaction assessment is to be recorded.

Local skin reactions (LSR) sum score is defined as the sum of intensity grades across all areas and signs per visit. Per sign, the most intense reaction is defined as the maximum intensity grade across visits.

The subject will assess burning and pain after application. The investigator or designee will explain the scores provided in Table 7-4 of the Protocol and the subject will tell which one to mark.

The local skin reaction assessment results will be presented in accordance with section 7 as the following outputs:

- frequency table for investigator assessment of lesional/perilesional area and subject's assessment of burning and pain after application by visit of assessment as scheduled in the Table 1 and most severe post-baseline assessment;
- shift table from baseline to each post-baseline visit value and most severe post-baseline value;
- descriptive statistics of LSR sum scores and their changes from baseline for lesional/perilesional area by visit

10. Pharmacokinetics

Samples for PK analysis will be collected through an untreated area of the skin, at the following time points:

- SV2: single time point
- Week 2 visit: single time point before IP application
- Week 4 visit: before the planned IP application at the visit and then at 1, 3, and 5 hours after the application
- Week 8 visit: single time point. Subject should not apply IP on the day of the Week 8 visit

Subjects are to be instructed to apply their daily dose of IP in the morning on the day before the Week 2, Week 4 and Week 8 visits. On the day of these visits, the subjects should not apply any

**MC2-01-C6_STATISTICAL ANALYSIS PLAN_Final 3.0_07 September 2020**

IP before the visit. A reminder to the subject may be needed a few days before the scheduled visit.

The samples will be assayed for concentrations of the active ingredients (BDP and CAL) and for their major metabolites (betamethasone 17-propionate and MC180, respectively).

All available concentration results will be summarised by analyte and time point using appropriate descriptive statistics. Individual concentration versus time curves will be plotted (linear and semi-log plots) using actual time points.

Measured PK concentrations will be presented using standard descriptive statistics as described in section 7. Additionally, geometric mean and CV(%) will be presented.

Non-quantifiable (BLQ) levels of the analyte will be substituted by LLOQ for descriptive summaries and graphical presentation.

Plasma PK parameters at Week 4 (AUC_{0-t}, AUC₀₋₅, C_{max}, and T_{max}) will be calculated. The PK parameters AUC₀₋₅ and C_{max} will be calculated using standard formulas inserting the LLOQ for non-quantifiable levels of the analyte. For a given analyte, the PK parameters AUC_{0-t} and T_{max} will be calculated if at least one post-dose time-point shows a quantifiable level of the analyte. PK parameter values will be rounded to the precision of the raw data from which it was derived (C_{max}) or to 3 significant digits (AUC_{0-t}, AUC₀₋₅). T_{max} will be rounded to two decimal places.

Pharmacokinetic Parameters Derivations:

AUC_{0-t} (pg*h/mL): The area under the curve spanning time interval from 0 to t (up to the last time point with measurable concentration above the quantification limit) will be calculated using the linear trapezoidal rule based on actual relative time of sampling.

- 1) Actual relative time of each sample will be derived as the difference between the datetime value of the corresponding sample and the datetime value of drug application, in hours. The time of the pre-dose sample will be set to 0.
- 2) For the calculation of AUC_{0-t} BLQ values before the first reported measurable concentration (including pre-dose) will be substituted by LLOQ. The BLQ values after the last evaluable concentration will be set to missing.
- 3) Linear trapezoidal method is used. The area under the curve is defined as the sum of trapezoids across all pairs of time points from pre-dose to 5h post-dose at Visit 3 / Week 4.

Linear trapezoidal rule:

The area of the trapezoid between the two data points (t₁, C₁) and (t₂, C₂) where C₂≥C₁ will be computed by:

**MC2-01-C6_STATISTICAL ANALYSIS PLAN_Final 3.0_07 September 2020**

$AUC_{t1-t2}=0.5(t_2-t_1)(C_1+C_2)$.

AUC₀₋₅ (pg*h/mL): The area under the time-concentration curve from 0 to 5 hours will be calculated in a similar way to AUC_{0-t} (pg*h/mL) while imputing the lower limit of quantification (LLoQ) for all concentrations below LLoQ.

C_{max} (pg/mL): Individual C_{max} values are directly determined from the plasma concentration time profiles of each subject as maximum of the observed concentration values after dosing. All BLQ values are substituted by LLOQ.

T_{max} (h): The time to attain C_{max}. If the same C_{max} concentration occurs at different time points, T_{max} is assigned to the first occurrence of C_{max}. If all concentrations are BLQ, T_{max} is not calculated.

The PK parameters will be summarised by analyte using standard descriptive statistics as described in section 7. Additionally, geometric mean and CV(%) will be presented for C_{max}, AUC_{0-t} and AUC₀₋₅.

11. Other Analyses

11.1. Physician global assessment

eCRF form: “PHYSICIAN’S GLOBAL ASSESSMENT OF PSORIASIS SEVERITY”.

Investigator ratings of disease severity (PGA) will be summarised by trial visit using frequency counts and percentages. The proportion of subjects with treatment success, defined as a minimum 2-point decrease from Baseline in the PGA on the trunk, limbs, and scalp will be summarised. Only subjects having at least moderate severity at baseline will be included in the summary of treatment success.

PGA results will be presented in accordance with section 7 by visit of assessment as scheduled in the Table 1 as the following outputs:

- descriptive statistics of measured values and changes from baseline by visit;
- number and proportion (95% CI) of subjects with treatment success, defined as a minimum 2-point decrease from Baseline in the PGA;
- Shift table by post-baseline visit compared to baseline for PGA.

11.2. Body surface area involvement

eCRF form: “BODY SURFACE AREA INVOLVEMENT ASSESSMENT”.

The investigator or designee will assess the extent of the subject’s psoriatic involvement on the scalp, neck, trunk and limbs (excluding face, genitals, and intertriginous areas).

**MC2-01-C6_STATISTICAL ANALYSIS PLAN_Final 3.0_07 September 2020**

The total psoriatic involvement on the scalp, neck, trunk and limbs will be recorded as a percentage of the total BSA, estimating that the surface of the subject's full, flat palm (including the five digits) correlates to approximately 1% of the total BSA.

Investigator assessment of BSA involvement for scalp and neck, trunk and/or limbs and total BSA involvement will be summarised in accordance with section 7 by visit of assessment as scheduled in the Table 1 as the following outputs:

- descriptive statistics of BSA values and changes from baseline by visit.

11.3. Psoriasis treatment convenience scale

eCRF form: “PSORIASIS TREATMENT CONVENIENCE SCALE”.

The aim of PTCS is to assess the impact and convenience of psoriasis treatment. The scale consists of 6 disease-specific, self-reported questions with a recall period of 1 week and rated on a 1-10 scale.

1. How easy was the treatment to apply to the skin? Answered by 1 = very difficult to 10 = very easy.
2. How greasy was the treatment when applying it to the skin? Answered by 1 = very greasy to 10 = not greasy.
3. How moisturised did your skin feel after applying the treatment? Answered by 1 = not moisturized to 10 = very moisturized.
4. How greasy did your skin feel after applying the treatment? Answered by 1 = very greasy to 10 = not greasy.
5. How much did treating your skin disrupt your daily routine? Answered by 1 = very disturbing to 10 = not disturbing.
6. Overall, how satisfied were you with the medical treatment? Answered by 1 = not satisfied to 10 = very satisfied.

Ranging from 5 to 50, a PTCS total score is the sum of the scores on questions 1 to 5. If more than two questions are not answered, the PTCS total score is missing. If one or two questions remain unanswered, the missing scores are replaced by the average of the answered scores for the summation.

Psoriasis treatment convenience scale results will be presented by visit of assessment as scheduled in the Table 1.

Psoriasis treatment convenience scale results will be presented by visit as the following summaries:

- descriptive statistics for patient ratings by question;
- descriptive statistics for PTCS total score

All ratings will be listed.

12. Reporting Conventions

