6.3 Dose Modification

Dose modification can only occur after Week 4.

Subjects classified as clear at any of the on-treatment visits may stop the IP treatment at the investigator's discretion. They should remain in the trial and attend all visits up to and including the follow-up visit. The IP will continue to be dispensed to the subject, and IP treatment may be restarted at the subject's discretion. The subject should not discontinue treatment themselves between visits but is only allowed to stop using the IP treatment on the advice of the investigator at a scheduled visit.

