7.6.2 HPA axis suppression/ ACTH challenge test

Adrenal function will be assessed in a challenge test with an intravenous dose of ACTH (cosyntropin). Measurement of serum cortisol levels pre- and post- stimulation with cosyntropin 0.25 mg is the accepted standard method used to evaluate adrenal suppression. The ACTH challenge test will be performed at SV2, Week 4 and Week 8 visits. The test consists of blood sampling starting between 7 and 9 am. Following the blood sample, an intravenous bolus injection of 0.25 mg cosyntropin is given at time zero ($t=0$ minutes). Serum cortisol concentration at $t=30$ minutes will reflect stimulation of the adrenal glands induced by cosyntropin.

The following criterion will define an adrenal suppression:

- the 30-minute post-stimulation level below 18 $\mu\text{g}/\text{dL}$ (500 nmol/l).

Week 4: If HPA axis suppression is noted at Week 4, the application with the MC2-01 cream should be discontinued. The subject should continue in the trial and the ACTH challenge test is repeated at the Week 8 visit. If HPA axis suppression is noted at Week 8, the ACTH challenge test has to be repeated at a follow-up visit 28 days (\pm 2 days) after the Week 8 visit (see [Section 7.12](#)).

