**MC2-01-C6_STATISTICAL ANALYSIS PLAN_Final 3.0_07 September 2020**

- Subject assessment of treatment convenience at Week 8 using a Psoriasis Treatment Convenience Scale.

4. Study Design

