APPENDIX 1 TFLs Shells

Programming note:

Report the following parameters: PTCS Total Score, Q1. How easy was the treatment to apply to the skin?, Q2. How greasy was the treatment when applying it to the skin?, Q3. How moisturized did your skin feel after applying the treatment?, Q4. How greasy did your skin feel after applying the treatment?, Q5. How much did treating your skin disrupt your daily routine?, Q6. Overall, how satisfied were you with the medical treatment?.

Report the following visits: Visit 2 / Week 2, Visit 3 / Week 4, Visit 5 / Week 8.

[figure not shown]

[figure not shown]
MC2-01-C6_STATISTICAL ANALYSIS PLAN_Final 3.0_07 September 2020

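### The Week 8 convenience summary pools subjects who used no cream in the scale's one-week recall period, with a bias of unknown sign and size

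*SAP*

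**What the plan says.** SAP 3.2.4 lists among the other endpoints "Subject assessment of treatment convenience at Week 8 using a Psoriasis Treatment Convenience Scale". SAP 11.3 gives the instrument: six "self-reported questions with a recall period of 1 week", each rated 1 to 10. Items 1 to 5 form the total: ease of application, greasiness during application, moisturisation afterwards, greasiness of the skin afterwards, and disruption of routine. A total is missing only if more than two items are blank. With one or two blanks, the average of the answered items is filled in.

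Table 14.4.3.1 uses the Safety population. Its programming note reads "Report the following visits: Visit 2 / Week 2, Visit 3 / Week 4, Visit 5 / Week 8", and its footnote counts valid measurements without reference to treatment status. The visit schedules (Protocol Table 7-1, SAP Table 1) mark the scale at Week 8 with no on-treatment condition. The only limit on collecting it is at the early termination visit (Protocol 7.13).

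Three protocol routes lead to Week 8 without current treatment:

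- **HPA suppression (Protocol 7.6.2).** "If HPA axis suppression is noted at Week 4, the application with the MC2-01 cream should be discontinued". Then: "The subject should continue in the trial and the ACTH challenge test is repeated at the Week 8 visit".
- **Clear skin (Protocol 6.3).** "Subjects classified as clear at any of the on-treatment visits may stop the IP treatment at the investigator's discretion". Then: "They should remain in the trial and attend all visits up to and including the follow-up visit". However, "IP treatment may be restarted at the subject's discretion".
- **Other discontinuation (Protocol 5.4).** Subjects who stop treatment are urged to attend at least the Week 8 visit.

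**The concern.** The scale asks about using the cream over the past week. A subject who applied none in that week has no such experience to report, yet the answer enters the same Week 8 mean and median as the answers of current users. The SAP has no rule that separates, flags or excludes these responses.

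The plan does expect such subjects. Table 14.1.1 has rows for treatment stopped because the subject was clear and because of HPA suppression at Week 4, and the compliance formula in SAP 9.1 removes approved off-treatment days. The convenience summary makes no matching allowance. What is at stake is whether the Week 8 row can be read as convenience of the cream in use. The HPA, calcium and pharmacokinetic endpoints are not affected.

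**Working it through.** **1. The plan's own figure.** SAP 11.3 gives a total from 5 to 50. Five items at 1 give 5 and five at 10 give 50, so the range reproduces and its width is 45.

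**2. Days off cream at Week 8.** Inputs are the visit days in Protocol Table 7-1: Week 4 = Day 28 ± 2, Week 6 = Day 42 ± 2, Week 8 = Day 56 ± 2. The gap is the Week 8 day minus the day of the stopping visit.

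- Stop at Week 6: 56 − 42 = 14 days. Shortest 54 − 44 = 10, longest 58 − 40 = 18.
- Stop at Week 4: 56 − 28 = 28 days. Shortest 54 − 30 = 24, longest 58 − 26 = 32.

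Even the shortest gap, 10 days, exceeds the 7-day recall. So without a restart, no application falls in the recall week. The Week 4 figure takes the stop as occurring at the visit. If the cortisol result came later, the stop would have to slip by at least 24 − 7 = 17 days to reach the recall week.

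**3. Weight of one such subject.** SAP 6.1 sets the interim after 7 treated subjects, so one rater is 1/7 = 14.3% of the row. At the planned 30 it is 1/30 = 3.3%. If k of n responders differ from the others by d points on average, the mean shifts by k × d / n. For one subject, each 10 points of difference moves the mean by 10/7 = 1.43 at n = 7 and by 10/30 = 0.33 at n = 30. The extreme at n = 7 is 45/7 = 6.43 in either direction.

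**4. Sign of the shift.** The documents do not say how an off-cream subject would answer, so every answer below is assumed. On-cream subjects score b on each item. One of 7 is off cream.

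| Off-cream answers | b | Off-cream total | On-cream total | Shift in mean |
|---|---|---|---|---|
| 10 on items 2, 4, 5; b on items 1, 3 | 7 | 44 | 35 | 9/7 = +1.29 |
| 10 on items 2, 4, 5; 1 on item 3; b on item 1 | 7 | 38 | 35 | 3/7 = +0.43 |
| As the row above | 9 | 40 | 45 | −5/7 = −0.71 |
| 10 on items 2, 4, 5; items 1, 3 blank | 7 | 50 | 35 | 15/7 = +2.14 |

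In the second pattern the difference is (b + 31) − 5b = 31 − 4b. It is zero at b = 7.75 and negative above that.

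The last row shows the blank-item rule at work. Three answers of 10 average 10, the two blanks are filled with 10, and the total is 30 + 20 = 50, the scale maximum.

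**5. How likely such a subject is.** No stopping rate is given. For an assumed off-cream share p, the chance of at least one is 1 − (1 − p)^n:

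| Assumed p | n = 7 | n = 30 |
|---|---|---|
| 5% | 30% | 79% |
| 10% | 52% | 96% |
| 20% | 79% | 99.9% |
| 30% | 92% | about 100% |

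**The case against.** A reader might infer that the Week 8 result is inflated, because someone applying nothing would report no greasiness and no disruption, which score 10. The documents do not support that. On the same reasoning, item 3 would be answered as not moisturised, which scores 1, and the net sign then depends on how current users score. A subject stopped for an adverse event might also score low.

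A reader might also infer that these subjects have no valid score at all. That goes too far. The questions are in the past tense and could be answered from last use. Items might be left blank, though nothing instructs this. The case report form is not among the documents, so a not-applicable option cannot be ruled out.

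Nor is every clear subject off cream. Stopping is discretionary and restarting is allowed, so that route counts only when no application fell in the recall week. The HPA route has no stated restart provision.

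Protocol 6.2 tells all subjects to apply cream the day before Week 8, which might suggest that everyone has recent use. That cannot describe a subject discontinued under Protocol 7.6.2.

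Some objections stand. The Week 2 and Week 4 rows are largely free of the problem, since Protocol 6.3 places dose modification after Week 4. Protocol 8.9.2 names Week 4 for this summary, which must be reconciled with the Week 8 endpoint. With 7 subjects, off-cream raters could be found by hand from the listings. Simple exclusion would select on events after baseline: clearing, suppression or adverse events.

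**Conclusion.** The point holds in a limited form. As written, the plan mixes into the Week 8 summary any responses from subjects who applied no cream during the recall week, and the blank-item rule can turn their partial answers into full totals. The bias has unknown sign and size. The illustrations run from −0.71 to +2.14 points for one subject of 7, and they rest on assumed answers. What follows from the documents is the timing (at least 10 days since last use after a stop by Week 6 without a restart) and the weight (14% of the row per subject at the interim).

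The number of such subjects is unknown. Severity is minor: this is a descriptive endpoint in an open-label, single-group trial, with no test, threshold or decision attached to it.

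**What to change.** In SAP 11.3 and Table 14.4.3.1:

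1. At each visit where the scale is completed, flag whether the subject applied cream in the previous 7 days. Derive the flag from the last application date (Listing 16.2.5.1), restart date (Listing 16.2.5.2) and missed doses (Listing 16.2.5.3).
2. Present the Week 8 item and total-score summaries for recent users as the main row, labelled as a selected on-treatment group.
3. Show non-users in a separate row with their count.
4. Keep every rating, with the flag, in Listing 16.2.9.9.

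The cost is SAP wording, one derived variable and an extra row, with no new data collection. SAP section 2 allows revision before the interim database lock and foresees a separate SAP for any final analysis. The downside is a smaller main row that no longer represents everyone treated, which is why non-users are shown and not dropped. No stopping or restart rule changes.
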